An investigator initiated open label study evaluating the efficacy and tolerability of application of Metaderm product for the treatment of psoriasis

Study Protocol & Statistical Analysis Plan

NCT03597620

November 5, 2018

[name]., Principal Investigator
University of Alabama at Birmingham
Birmingham, AL 35294

An investigator initiated open label study evaluating the efficacy and tolerability of application of Metaderm product for the treatment of psoriasis

PI: [name]

Sponsor : Procter & Gamble

Introduction:

Psoriasis vulgaris is a common inflammatory condition of the skin that results in well-demarcated, scaly, erythematous, itchy plaques. In the United States, psoriasis remains a common, immune-mediated disease, affecting 7.4 million adults. (1) Often topical prescription medications are used as first line treatment for moderate psoriasis. Some topical medications have side effects and risk with long time use, thus not ideal for extensive and indefinite amount of time. Conversely, over-the-counter emollient treatments are readily available, safe and potentially efficacious. This study is design to test the safety and efficacy of topical application of the Metaderm product cream. The Metaderm cream is non-prescription, natural product.

Study objectives

Primary objective

The Primary efficacy and end point will be the mean percentage change in the product of sPGA and BSA (PGAxBSA) from baseline to week 12. The PGA x BSA is an assessment tools used to calculating disease severity and maybe more likely to differentiate among people with less disease severity (Walsh)

Secondary objective

The secondary efficacy and end point will be the percentage improvement in DLQI

Study Design

Study Outline

This is an open-label pilot study aimed at evaluating the efficacy and safety of treating psoriasis using the Metaderm product. The inclusion and exclusion criteria as listed below. Study designed into 3 subgroups:

- 1) 5 patients with plaque psoriasis 3-10% BSA
- 2) 5 patients with stable dose of biologic treatment and have plaque psoriasis with 3-10% BSA
- 3) 5 patients with scalp psoriasis

Number of subjects:

Total of 15 eligible patients will be enrolled. Patients will be treated for duration of 12 weeks. During the treatment phase patients will be evaluated every 4 weeks. All patients will be treated with the active medication, there will be no placebo arm in the study.

Visit Schedule

Screening Period

Patient eligibility will be determined within 28 days prior to enrollment in the study. Subjects who meet the inclusion and exclusion criteria may proceed to the baseline visit.

Study Visits

Subjects will report to the investigational site for disease and safety assessments every 4 weeks for total of 12 Weeks. Patients will have photos taken of 1-3 target lesions at baseline , W4 , W8, and W12 . Patient will complete the Itch Severity Scale (ISS, Visual Analogue Scale (VAS) and Dermatology Quality of Life Index (DLQI) questionnaires at every visit. Patient will have a Psoriasis Area and Severity Index (PASI), Static Physicians Global Assessment (sPGA) and Body Surface Area (BSA) evaluation at every visit.

Dosing schedule

15 eligible patients will be enrolled. Patient will be treated for 12 weeks. There will be a total of five visits: screening, baseline, w4, w8 and w12. Metaderm cream will be applied topically twice a day to all active lesions. The metaderm scalp spray will be applied daily to the affected areas on the scalp. Patients will be provided with metaderm cleanser, can be use daily. For the subgroup for scalp psoriasis, patient will use the shampoo Head & Shoulders formula with 1% Pyrithione Zinc as the active ingredient

Discontinuation of the Study

The study may be discontinued at the discretion of the investigator at any time without replacement

STUDY ENTRY CRITERIA

Patients will be recruited from the university hospital clinic as well as resident's continuity clinics

Inclusion Criteria for patients with plaque psoriasis 3-10% BSA

Subjects must satisfy the following criteria to be enrolled in the study:

1. Must be in general good health (except for disease under study) as judged by the Investigator, based on medical history, physical examination, clinical laboratories, and urinalysis. (NOTE: The definition of good health means a subject does not have uncontrolled significant co-morbid conditions).
2. Patients 18 and older
3. Give written informed consent prior to any study procedures being conducted, and candidates will authorize the release and use of protected health information (PHI)
4. Be willing and consent to having photos taken of their skin
5. Diagnosis of chronic plaque psoriasis that has been present for at least 6 months prior to baseline

6. Plaque psoriasis involving at least 3-10% of the patient's body surface area
7. Must have discontinued all systemic therapies for the treatment of psoriasis or psoriatic arthritis (at least 4 weeks or 5 half-lives, and biologics 6 months) prior to baseline visit
8. Must have discontinued all topical therapies for the treatment of psoriasis at least 2 weeks prior to baseline visit
9. Subjects must have discontinued UV therapy at least 2 weeks prior to baseline and PUVA at least 4 weeks prior to baseline.
10. Subjects must be in good general health without significant uncontrolled comorbidities, other than psoriasis, as determined by the investigator based on exam findings, medical history, and clinical laboratories. Patients with stable mild renal insufficiency are eligible for enrolling in this trial.
11. Females of childbearing potential must use an approved birth control method while receiving treatment and for 28 days following the investigational product and there must be a documented negative pregnancy tests prior to initiating treatment. Approved birth control methods include hormonal contraception (oral, injection, implant, transdermal patch, vaginal ring), intrauterine device, tubal ligation (tying your tubes), partners vasectomy, or male or female condoms that are not made of natural materials PLUS a diaphragm with spermicide, cervical cap with spermicide, or a contraceptive sponge with spermicide. Females not of child bearing potential are defined as being at least 1 year postmenopausal or surgically sterile (bilateral tubal ligation, bilateral oophorectomy and/or hysterectomy).

Inclusion Criteria with stable dose of biologic treatment and have plaque psoriasis 3-10 %BSA

Subjects must satisfy the following criteria to be enrolled in the study:

1. Must be in general good health (except for disease under study) as judged by the Investigator, based on medical history, physical examination, clinical laboratories, and urinalysis. (NOTE: The definition of good health means a subject does not have uncontrolled significant co-morbid conditions).
2. Patients 18 and older
3. Give written informed consent prior to any study procedures being conducted, and candidates will authorize the release and use of protected health information (PHI)
4. Be willing and consent to having photos taken of their skin

5. Diagnosis of chronic plaque psoriasis that has been present for at least 6 months prior to baseline
6. Stable dose of biologic therapy for the last 6 months prior to screening visit
7. Plaque psoriasis involving at least 3-10% of the patient's body surface area
8. Must have discontinued all topical therapies for the treatment of psoriasis at least 2 weeks prior to baseline visit
9. Subjects must have discontinued UV therapy at least 2 weeks prior to baseline and PUVA at least 4 weeks prior to baseline.
10. Subjects must be in good general health without significant uncontrolled comorbidities, other than psoriasis, as determined by the investigator based on exam findings, medical history, and clinical laboratories. Patients with stable mild renal insufficiency are eligible for enrolling in this trial.
11. Females of childbearing potential must use an approved birth control method while receiving treatment and for 28 days following the investigational product and there must be a documented negative pregnancy tests prior to initiating treatment. Approved birth control methods include hormonal contraception (oral, injection, implant, transdermal patch, vaginal ring), intrauterine device, tubal ligation (tying your tubes), partners vasectomy, or male or female condoms that are not made of natural materials PLUS a diaphragm with spermicide, cervical cap with spermicide, or a contraceptive sponge with spermicide. Females not of child bearing potential are defined as being at least 1 year postmenopausal or surgically sterile (bilateral tubal ligation, bilateral oophorectomy and/or hysterectomy).

Inclusion Criteria for patients with scalp psoriasis

Subjects must satisfy the following criteria to be enrolled in the study:

1. Must be in general good health (except for disease under study) as judged by the Investigator, based on medical history, physical examination, clinical laboratories, and urinalysis. (NOTE: The definition of good health means a subject does not have uncontrolled significant co-morbid conditions).
2. Patients 18 and older
3. Give written informed consent prior to any study procedures being conducted, and candidates will authorize the release and use of protected health information (PHI)

4. Be willing and consent to having photos taken of their skin
5. Diagnosis of chronic plaque psoriasis that has been present for at least 6 months prior to baseline
6. Plaque psoriasis involving the scalp
7. Body plaque psoriasis cannot exceed 10 %BSA
8. Must have discontinued all systemic therapies for the treatment of psoriasis or psoriatic arthritis (at least 4 weeks or 5 half-lives, and biologics 6 months) prior to baseline visit
9. Must have discontinued all topical therapies for the treatment of psoriasis at least 2 weeks prior to baseline visit
10. Subjects must have discontinued UV therapy at least 2 weeks prior to baseline and PUVA at least 4 weeks prior to baseline.
11. Subjects must be in good general health without significant uncontrolled comorbidities, other than psoriasis, as determined by the investigator based on exam findings, medical history, and clinical laboratories. Patients with stable mild renal insufficiency are eligible for enrolling in this trial.
12. Females of childbearing potential must use an approved birth control method while receiving treatment and for 28 days following the investigational product and there must be a documented negative pregnancy tests prior to initiating treatment. Approved birth control methods include hormonal contraception (oral, injection, implant, transdermal patch, vaginal ring), intrauterine device, tubal ligation (tying your tubes), partners vasectomy, or male or female condoms that are not made of natural materials PLUS a diaphragm with spermicide, cervical cap with spermicide, or a contraceptive sponge with spermicide. Females not of child bearing potential are defined as being at least 1 year postmenopausal or surgically sterile (bilateral tubal ligation, bilateral oophorectomy and/or hysterectomy).

Exclusion Criteria

The presence of any of the following will exclude a subject from enrollment:

13. Other than disease under study, any clinically significant (as determined by the Investigator) cardiac, endocrinologic, pulmonary, neurologic, psychiatric, hepatic, renal, hematologic, immunologic disease, or other major disease that is currently uncontrolled.

14. Any condition, including the presence of laboratory abnormalities, which would place the subject at unacceptable risk if he/she were to participate in the study.
15. Prior history of suicide attempt at any time in the subject's life time prior to screening or randomization, or major psychiatric illness requiring hospitalization within the last 3 years.
16. Pregnant or breast feeding.
17. Active substance abuse or a history of substance abuse within 6 months prior to Screening.
18. Use of any investigational drug within 4 weeks prior to randomization, or 5 pharmacokinetic/pharmacodynamic half lives, if known (whichever is longer).
19. Prior treatment with the investigational product
20. Unable to comply with the protocol (as defined by the Investigator; i.e. drug or alcohol abuse or history of noncompliance)
21. Any other dermatologic conditions that prohibit or confound the ability of the investigator to interpret skin and/or nail exam findings.
22. Patients who will be unable to avoid the use of systemic steroids, excluding intranasal or inhaled steroids that will be permitted, for the duration of the trial

STUDY PROCEDURES & TREATMENT PLAN GUIDELINES

Informed Consent:

A written, signed informed consent form (ICF) and written authorization to release and use PHI, will be obtained prior to performing any tests or evaluations under this protocol. Patients will have the option to ask questions and will be given at least 24 hours to review the ICF before signing. Patients may request the 24 hour review to be waived due to work or travel constraints.

See Protocol Flowchart for detailed timing of tests and evaluations.

General Concomitant Therapy:

Subjects should advise the investigator if they start taking any new medications, including over the counter and complementary and alternative medications.

Concomitant Therapy

Concomitant medications for psoriasis will not be permitted

SAFETY PLAN

Clinical Safety Assessments

The following clinical safety assessments will be performed: (See study flowchart)

- Physical examinations
- Vital signs (temperature, heart rate, blood pressure, and weight)
- Monitoring for adverse events
- Monitoring for concomitant therapy

Laboratory Safety Assessments

The following laboratory tests will be performed at screening, baseline:

- Urine pregnancy test, if applicable.

Test / Evaluation	Screening	Visit 1 W k 0	Visit 2 Wk 4	Visit 3 Wk 8	Visit 4 Wk 12
Informed Consent	X				
Inclusion/exclusion criteria reviewed	X	X			
Medical History	X				
Concomitant medications	X	X	X	X	X
Physical Exam	X				
Vital Signs	X	X	X	X	X
Urine pregnancy test	X	X			
Adverse Events	X	X	X	X	X
Photos of Target lesions	x	X	x	x	X
PASI	x	X	x	x	x
BSA	x	X	x	x	x
sPGA	x	x	x	x	x
ISS	X	X	X	X	X
PSSI	X	X	X	X	X
VAS	X	X	X	X	X
DLQI	X	X	X	X	X
IP dispensing		X	X	X	X
IP accountability			X	X	X

SAFETY REPORTING

Adverse Event

An adverse event (AE) is any noxious, unintended, or untoward medical occurrence occurring at any dose that may appear or worsen in a subject during the course of a study. It may be a new intercurrent illness, a worsening concomitant illness, an injury, or any concomitant impairment of the subject's health, including laboratory test values (as specified by the criteria below), regardless of etiology. Any medical condition that was present prior to study treatment and that remains unchanged or improved should not be recorded as an AE. If there is a worsening of that medical condition this should be considered an AE. A diagnosis or syndrome should be recorded on the AE page of the Case Report Form rather than the individual signs or symptoms of the diagnosis or syndrome.

All AEs will be recorded by the Investigator(s) from the time of signing the informed consent through the end of the designated follow-up period.

Serious adverse event

A serious adverse event (SAE) is any AE which:

- Results in death
- Is life-threatening (i.e., in the opinion of the Investigator(s) the subject is at immediate risk of death from the AE)
- Requires inpatient hospitalization or prolongation of existing hospitalization
- Results in persistent or significant disability/incapacity (a substantial disruption of the subject's ability to conduct normal life functions)
- Is a congenital anomaly/birth defect
- Constitutes an important medical event

Important medical events are defined as those occurrences that may not be immediately life threatening or result in death, hospitalization, or disability, but may jeopardize the subject or require medical or surgical intervention to prevent one of the other outcomes listed above. Medical and scientific judgment should be exercised in deciding whether such an AE should be considered serious.

Events not considered to be SAEs are hospitalizations which: were planned before entry into the clinical study; are for elective treatment of a condition unrelated to the studied indication or its treatment; occur on an emergency outpatient basis and do not result in admission (unless fulfilling other criteria above); are part of the normal treatment or monitoring of the studied indication and are not associated with any deterioration in condition.

If an AE is considered serious, both the AE pages of the CRF and the SAE Report Form must be completed.

For each SAE, the Investigator(s) will provide information on severity, start and stop dates, relationship to study drug, action taken regarding study drug, and outcome.

Classification of severity

For both AEs and SAEs, the investigator(s) must assess the severity of the event. The AEs will be evaluated for severity according to the following scale:

Grade 1 = Mild

Grade 2 = Moderate

Grade 3 = Severe

Classification of Relationship/Causality of adverse events (SAE/AE) to study drug

The Investigator(s) must determine the relationship between the administration of study drug and the occurrence of an AE/SAE as Not Suspected or Suspected as defined below:

Not suspected: The temporal relationship of the adverse event to study drug administration makes **a causal relationship unlikely or remote**, or other medications, therapeutic interventions, or underlying conditions provide a sufficient explanation for the observed event

Suspected: The temporal relationship of the adverse event to study drug administration makes **a causal relationship possible**, and other medications, therapeutic interventions, or underlying conditions do not provide a sufficient explanation for the observed event.

Immediate reporting of serious adverse events

Any AE that meets the any criterion for a SAE requires the completion of an SAE Report Form in addition to being recorded on the AE pages of the CRF. The Investigator(s) is required to ensure that the data on these forms is accurate and consistent. This applies to all SAEs, regardless of relationship to study drug, that occur during the study, those made known to the Investigator(s) within 30 days after a subject's last dose of study drug, and those made known to the investigator(s) at anytime that are suspected of being related to study drug.

The SAE must be reported immediately (i.e., within 24 hours of the Investigators' knowledge of the event)

The Investigator(s) is responsible for informing the Institutional Review Board/Ethics Committee (IRB/IEC) of the SAE and providing them with all relevant initial and follow-up information about the event. The Investigator(s) must keep copies of all SAE information, including correspondence with Celgene and the IRB/IEC, on file. All SAEs that have not resolved upon discontinuation of the subject's participation in the study must be followed until either the event resolves completely, stabilizes/resolves with sequelae, or returns to baseline (if a baseline value is available).

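### In groups 1 and 3 the systemic washout depends on why a drug was prescribed, so a patient who recently started, changed or stopped a psoriasis-active drug for another controlled disease can be enrolled

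*Combined protocol and SAP*

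**What the plan says.** The washout for group 1 (Inclusion Criteria for patients with plaque psoriasis 3-10% BSA, item 7) and group 3 (Inclusion Criteria for patients with scalp psoriasis, item 8) is worded identically: "Must have discontinued all systemic therapies for the treatment of psoriasis or psoriatic arthritis". A parenthesis then sets the intervals before baseline: 4 weeks or 5 half-lives in general, and 6 months for biologics. The limit is the indication.

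During the study, the Concomitant Therapy section says "Concomitant medications for psoriasis will not be permitted", which is again limited by indication. For everything else, General Concomitant Therapy says "Subjects should advise the investigator if they start taking any new medications". The flowchart records concomitant medications at screening and at every visit.

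Two rules do not depend on indication. Exclusion 22 removes "Patients who will be unable to avoid the use of systemic steroids, excluding intranasal or inhaled steroids that will be permitted", for the length of the trial. The light-therapy item says "Subjects must have discontinued UV therapy at least 2 weeks prior to baseline and PUVA at least 4 weeks prior to baseline".

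Group 2 must be on a biologic: "Stable dose of biologic therapy for the last 6 months prior to screening visit". No indication is named there.

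The primary endpoint is the mean percentage change in sPGA x BSA from baseline to week 12. There are three groups of 5, 15 patients in all, and no placebo arm. The document does not say whether the mean is taken within each group or over all 15.

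**The concern.** A pre-baseline washout makes sense only if a recent systemic drug can still move the outcome after baseline. That carry-over comes from the drug and does not depend on the diagnosis that led to it. A patient who recently began a psoriasis-active agent for another immune-mediated disease may improve over the 12 weeks because of that agent. One who recently stopped it may worsen. Both satisfy the washout item as written.

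With no control group, change from baseline is the only evidence of efficacy, so such a change would be read as the effect of the study product. The direction is not fixed: a recent start would tend to flatter the product and a recent stop to penalise it.

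**Working it through.** **Step 1: does another criterion remove this patient?** Take a patient in group 1 or 3 whose other immune-mediated disease is controlled on a non-steroid systemic drug that also acts on psoriasis.

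- Washout item 7 or 8: not triggered, because the drug is not for psoriasis or psoriatic arthritis. The words on biologics sit inside the parenthesis of the same sentence, so the literal reading keeps the indication limit. A site could read them as covering any biologic; for biologics the text is ambiguous.
- Good-health items (1 and 10 in group 1; 1 and 11 in group 3) and exclusion 13: these remove uncontrolled disease only.
- Exclusion 14: concerns unacceptable risk. Exclusion 18: investigational drugs. Exclusion 21: other skin conditions.
- Exclusion 22: systemic steroids only, and forward-looking. A steroid course for another disease that ended just before baseline is caught neither by it nor by item 7 or 8.

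No written criterion expressly bars the patient.

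**Step 2: weight of one patient.** The document gives no standard deviation, effect size or prevalence, so it has no figure to reproduce beyond 5 + 5 + 5 = 15. In an unweighted mean of n patients, one patient who differs from the mean of the others by D percentage points moves the mean by D/n. The weight is 1/5 = 20% or 1/15 = 6.7%.

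| D (assumed, points) | shift, n = 5 | shift, n = 15 |
|---|---|---|
| 20 | 4 | 1.3 |
| 50 | 10 | 3.3 |
| 75 | 15 | 5.0 |
| 100 | 20 | 6.7 |

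Example, all values assumed and improvement counted as positive:

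- Others improve 20%, one improves 75%: (4 x 20 + 75)/5 = 31%; (14 x 20 + 75)/15 = 23.7%.
- Others improve 20%, one worsens 50%: (4 x 20 - 50)/5 = 6%; (14 x 20 - 50)/15 = 15.3%.

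**Step 3: chance of meeting such a patient.** If a share p of candidates take such a drug, the chance of at least one among the 10 patients of groups 1 and 3 is 1 - (1 - p)^10. For assumed p of 1%, 2%, 5% and 10% this is 9.6%, 18.3%, 40.1% and 65.1%. Only those whose drug changed recently matter much for bias, so the chance of a harmful case is lower.

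**Step 4: scale against ordinary imprecision.** The 95% half-width of a mean is t(0.975, n-1) x SD/sqrt(n). For assumed SDs of 20 to 50 points it is 24.8 to 62.1 points at n = 5 and 11.1 to 27.7 points at n = 15. The shifts in the first example, 11 and 3.7 points, lie inside these intervals.

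**The case against.** A reader might infer that every drug rule in the protocol turns on indication. It does not: exclusion 22 and the light-therapy washout apply whatever the reason for treatment.

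A reader might also infer that any patient on such a drug distorts the result. The endpoint is change within a patient, so a drug at a long-stable dose is largely in the baseline value already. The problem needs a drug started, changed or stopped near baseline or on study. Such a patient may well have disease that is not yet controlled, and the investigator could then exclude them under the good-health items or exclusion 13. That safeguard is real but discretionary; the written rule still admits a patient judged controlled.

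It is tempting to say that groups 1 and 3 are meant to be free of biologics and that the contrast with group 2 is spoiled. The document does not use that label, defines group 3 by scalp disease, and plans no comparison between groups. Nor does the unnamed indication in group 2's biologic item cause bias by itself: a stable biologic without psoriasis activity would not move change from baseline.

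The size is illustrative. The inputs are assumed, a five-patient mean is not stated to be primary, and the pooled shift is one third as large. In a pilot this small, sampling error exceeds the example shift. That stands, but this error is systematic and can be avoided by wording. Because medications are recorded at every visit, a case among 15 would also be visible; the plan does not say what would then be done with it.

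**Conclusion.** The gap is real and modest. The washout in groups 1 and 3 lets in a patient who recently started, changed or stopped a psoriasis-active systemic drug for another controlled disease, and the study has no control against which to separate that drug's effect. In the assumed first example the mean moves from 20% to 31% if it is taken within a group of five, or to 23.7% if taken over 15. How often this would happen, and in which direction, cannot be found from the document.

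It does not follow that the trial's drug rules are indication-based throughout, that stable co-medication biases the endpoint, or that an on-study ban is needed. Two passages do need reconciling whatever is decided here. The ban on psoriasis medication, read literally, conflicts with group 2 continuing its biologic. Exclusion 22 looks only forward, while the washout items reach systemic steroids before baseline only when they were given for psoriasis or psoriatic arthritis.

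**What to change.** 1. In group 1 item 7 and group 3 item 8, make eligibility depend on not having taken a systemic agent with known activity in psoriasis, whatever the indication, within the intervals those items already state. List the agents or classes meant, so that sites apply the rule alike. This limits enrolment only; nobody is asked to stop a drug.
2. For drugs started or changed on study, add no new ban. Use the concomitant-medication record already taken at each visit to flag affected patients by a rule fixed before analysis. Report the primary mean with and without them, with the mean over all patients as the main result. In the same place, state whether the primary mean is per group or pooled.
3. Reconcile the Concomitant Therapy sentence with group 2's required biologic, and reconcile exclusion 22 with the washout items for systemic steroids. The choice of clinical rule is for the investigator and sponsor.

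Cost: two reworded entry items, a short analysis statement and two clarifications. No new data are collected. A few patients with other immune-mediated disease become ineligible, which may slow recruitment slightly.

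### Group 2 has no pre-baseline rule for non-biologic systemic drugs, so the fading effect of one stopped just before baseline could count against the product

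*Combined protocol and SAP*

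**What the plan says.** The three subgroups have separate inclusion lists and share one exclusion list.

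- **Group 1** (plaque psoriasis, 3-10% BSA), item 7: before baseline, patients must have "discontinued all systemic therapies for the treatment of psoriasis or psoriatic arthritis (at least 4 weeks or 5 half-lives", with six months for biologics.
- **Group 3** (scalp psoriasis), item 8: the same requirement, "at least 4 weeks or 5 half-lives, and biologics 6 months".
- **Group 2** (stable biologic, 3-10% BSA), item 6: "Stable dose of biologic therapy for the last 6 months prior to screening visit". Item 8 keeps the topical washout ("Must have discontinued all topical therapies for the treatment of psoriasis at least 2 weeks prior to baseline visit") and item 9 keeps the light-therapy washout ("Subjects must have discontinued UV therapy at least 2 weeks prior to baseline and PUVA at least 4 weeks prior to baseline"). None of its eleven items mentions a non-biologic systemic drug.

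Under Concomitant Therapy, for all groups: "Concomitant medications for psoriasis will not be permitted". Under General Concomitant Therapy: "Subjects should advise the investigator if they start taking any new medications".

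The primary endpoint is the mean percentage change in sPGA x BSA from baseline to week 12. All patients receive the product and there is no placebo arm.

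**The concern.** A change from baseline can be read as a product effect only if other treatment effects are reasonably steady when baseline is measured. The plan applies that principle to topicals and light therapy in all three groups, and to systemic drugs in groups 1 and 3. For non-biologic systemics in group 2 it does not, and it gives no reason for the difference. A possible explanation, which is an inference, is that group 1's item 7 was left out of group 2 as a whole because its biologic clause could not apply, and the non-biologic clause went with it.

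The on-study ban makes the gap more than a missing detail, because it forces a patient taking such a drug for psoriasis to stop without fixing a date. A drug still working at baseline holds the baseline score down. If its effect wears off during the 12 weeks, the score rises and the product appears to do worse than it did. There is no control arm to separate the two, and with five patients in the group a single case would be visible in the mean.

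**Working it through.** **1. Plan's own figure.** Three subgroups of 5 give 3 x 5 = 15, the stated total. No power or precision basis is given, and this point does not depend on one.

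**2. Pre-baseline rules side by side.**

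| Prior treatment | Group 1 | Group 2 | Group 3 |
|---|---|---|---|
| Topical | off 2 weeks (item 8) | off 2 weeks (item 8) | off 2 weeks (item 9) |
| UV / PUVA | off 2 / 4 weeks (item 9) | off 2 / 4 weeks (item 9) | off 2 / 4 weeks (item 10) |
| Biologic | off 6 months (item 7) | stable 6 months (item 6) | off 6 months (item 8) |
| Non-biologic systemic | off 4 weeks or 5 half-lives (item 7) | **no item** | off 4 weeks or 5 half-lives (item 8) |

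**3. Could a shared rule fill the empty cell?**

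- Exclusion 18 sets an interval for investigational drugs only.
- Exclusion 22 ("Patients who will be unable to avoid the use of systemic steroids") concerns steroids only, and looks forward over the trial.
- The Concomitant Therapy ban starts on study and sets no interval before it.
- The General Concomitant Therapy sentence asks about drugs started, not stopped.
- The flowchart records concomitant medications at screening and baseline, so a drug stopped between those visits would be seen. No criterion acts on it.

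Nothing fills it. A group 2 patient who stops a non-biologic systemic the day before baseline is eligible as written.

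**4. Illustrative size.** The documents give neither the sPGA scale nor the size of any fading effect. Assume whole sPGA steps, one affected patient, a one-step worsening from baseline score a, and BSA b unchanged:

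(change in product) / baseline = [(a + 1)b - ab] / ab = 1/a, so BSA cancels.

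Assume also that the endpoint is the mean of per-patient percentages. The shift in the mean is then (1/a)/5 in group 2 and (1/a)/15 if the three groups are pooled. The plan specifies neither the averaging nor the pooling.

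| sPGA step | Patient's change | Shift, n = 5 | Shift, n = 15 |
|---|---|---|---|
| 1 to 2 | +100% | 100/5 = +20.0 points | 100/15 = +6.7 points |
| 2 to 3 | +50% | 50/5 = +10.0 points | 50/15 = +3.3 points |
| 3 to 4 | +33.3% | 33.3/5 = +6.7 points | 33.3/15 = +2.2 points |

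For example, if the mean change without any fading were -20% (assumed), the middle row gives -20 + 10 = -10% in group 2 and -20 + 3.3 = -16.7% pooled. With no affected patient the shift is zero.

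**5. Drug remaining at baseline**, 2^(-days/half-life), for assumed half-lives. One day after stopping, 2^-2 = 25% remains at a half-life of 0.5 days and 2^-0.1 = 93.3% at 10 days. After 5 half-lives, 2^-5 = 3.1% remains. After 28 days at a 10-day half-life, 2^-2.8 = 14.4% remains. These are drug levels, not clinical effects, and do not measure bias in PGAxBSA. They show only why a new group 2 rule should take the longer of the two limbs.

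**The case against.** The harm depends on a chain of conditions. A patient on a biologic stable for six months must also be taking a non-biologic systemic, stop it shortly before baseline, still benefit at baseline, and lose that benefit within 12 weeks. The documents give no frequency for any link, and the sizes above come from assumed steps. The bias runs against the product, so it would not create a false claim of efficacy. In a 15-patient open-label pilot with no stated test or success threshold, no decision is shown to change. All of this stands and limits the weight of the point. It does not fill the empty cell.

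Two further objections shape the remedy. First, the ban names psoriasis and not psoriatic arthritis, so a patient on a steady arthritis systemic can arguably stay on it now with nothing fading. A forced washout could create the instability that it is meant to prevent. This stands, and a stable dose should be an equal option for those patients. Second, read literally, the ban also conflicts with the continuing biologic of all five group 2 patients. That stands too, and the exception belongs in the fix.

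A reader might infer that a washout would remove any disease flare after withdrawal. Nothing in the documents shows that disease is steady after 4 weeks or 5 half-lives, so the claim is only that the interval reduces carry-over of drug. A reader might also extend the criticism to the wording in groups 1 and 3, which does not say which limb governs. That is a separate question and adds no weight here.

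**Conclusion.** The omission is real on the text, and no shared criterion closes it. Its consequence is conditional: if a group 2 patient stops a non-biologic systemic just before baseline and its effect fades, the rise in PGAxBSA counts against the product and cannot be separated from it. One such patient would shift the group 2 mean by about +7 to +20 points (+10 for sPGA 2 to 3), under the assumptions of whole sPGA steps, unchanged BSA and a mean of per-patient percentages.

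A reader might conclude that the group 2 result will be biased. The documents do not support that, because the number of affected patients is unknown and may be zero. The point is a minor-to-moderate eligibility correction, worth making because it is specific and cheap. The lack of a control arm is a separate limit that it leaves in place.

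**What to change.** Change group 2 only. Add a criterion along these lines:

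> Must have discontinued all non-biologic systemic therapies for psoriasis at least 4 weeks or 5 half-lives (whichever is longer) prior to baseline; the biologic in item 6 is continued. A non-biologic systemic taken for psoriatic arthritis must either be washed out by the same rule or be at a stable dose for 6 months before screening and held through week 12.

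Under Concomitant Therapy, name the item 6 biologic, and any such stable arthritis drug, as exceptions to the ban.

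**Cost.** Sample size, visits and endpoint do not change. A few patients wait longer before baseline. Eligibility is determined within 28 days before enrollment, so for a drug stopped at screening the 4-week interval uses the whole window and leaves no slack. Above a half-life of 28/5 = 5.6 days, the 5-half-life limb exceeds the window. Such a drug must be stopped before screening, or consent taken first and the patient re-screened. A patient on an arthritis systemic who meets neither option could not enter.
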